Our clinic-based studies yielded key findings related to biomarkers, Sound Sweeps performance, and predictors of therapeutic sensitivity to a full course of TCT. **First**, baseline levels of EAIP predicted TCT learning during 1h of Sound Sweeps. **Second**, SZ patients exhibited clinical, neurocognitive and functional gains after 30h of TCT, and changes in EAIP during the first hour of Sound Sweeps testing predicted neurocognitive and clinical gains after a full 30h course of TCT. In total, these findings with memantine, EAIP, TCT learning, and clinical outcomes provide a strong empirical and conceptual framework for a mechanistically-based hypothesis to be tested via the proposed randomized, placebo-controlled 30h pilot trial of (memantine+TCT) vs. (placebo+TCT). Via the below Aims, this application provides efficient pilot testing of this PACT strategy in antipsychotic-medicated SZ patients, using Go/No-Go criteria to inform a future, fully-powered “Confirmatory Efficacy trial”:

AIM 1 – Replicate previous findings of memantine target engagement on TCT learning: In two, 1h tests, determine if memantine increases Sound Sweeps TCT learning in SZ patients (n=54) vs. placebo.

AIM 2 – Test clinical, neurocognitive and functional impact of memantine on TCT, and its relationship to target engagement: In a 30-session course of TCT over 10 weeks, determine if memantine augments the magnitude, rate and/or durability of TCT-induced gains, and whether these gains are associated with target engagement.

AIM 3 – Explore biomarkers of memantine-induced gains: Determine whether higher basal levels of EAIP (and related functional and neurophysiological measures) or changes in these measures across the first hour of Sound Sweeps predict greater sensitivity to memantine-enhanced clinical, neurocognitive or functional gains among SZ patients receiving combined memantine+TCT.

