General Methods: Environment: Subjects are screened, tested and undergo TCT at the UCSD Medical Center. Participants are 18-55 y.o. AP-medicated (stable regimen \geq 1 month, in active outpatient treatment) patients with a primary diagnosis of SZ or schizoaffective disorder (depressed type), recruited and consented at UCSD as per^{49,59,74}. Study inclusion/exclusion criteria are detailed in "**Protection of Human Subjects**". Screening includes a confirmatory diagnostic assessment (M.I.N.I. 6.0), a general medical, psychiatric and substance history, physical exam by an M.D., EKG, vision and hearing tests, urine toxicology and pregnancy test (UTox/P). All medications and changes are recorded (AP doses in chlorpromazine equivalents; quantifying anticholinergic burden⁹⁵ as in^{33,48,49}). Medication patterns of our last \approx 100 SZ subjects are published elsewhere^{49,74,96}.

Design (Fig. 5). Enrolled patients complete clinical, neurocognitive and functional measures and candidate biomarkers (EEG, QuickSIN, WIN) tested in Sound Sweeps at baseline, and then assigned to PBO vs. MEM arms (n=27/arm) using stratified random sampling (over sex, age and high/low Test 1 (baseline) APS learning) blind to arm identity. Stratifying for baseline APS learning should increase the sensitivity of the primary target engagement metric. Test 2 follows \approx 5-7 days later, after either PBO or MEM (20 mg po). Tests 1-2 are used to assess target engagement (Aim 1: MEM-enhanced APS learning) as well as MEM effects on ERP/EEG, auditory discrimination (QuickSIN, WIN) and neurocognitive measures (Aim 3: Biomarkers). Our design allows for 20% attrition from enrollment (n=69) to completion of target engagement testing (n=54).

For Aim 2, all participants will be titrated up to 20 mg MEM or Placebo over a 3-week period and concurrently begin TCT 3 d/week (M-W-F) for 1-h/d (recognizing the need for flexibility, T-Th are "make-up days"), and continues until a subject completes 30-h (\approx 10-12 weeks). TCT is delivered by trained staff (see below). Patients and staff are blind to study arm; staff are blind to patients' baseline, interval, and post-intervention assessments.

[figure not shown]

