Biomarkers from Tests 1-2 will be assessed as predictors of target engagement (Aim 1) and PACT sensitivity (Aim 2); in some cases, these measures will also inform mechanistic models for PACT: 1. **MEM-enhanced APS learning is both an outcome measure** (Aim 1, “target engagement”) and **candidate predictor** of clinical outcome (Aim 2); 2. Baseline and MEM-enhanced **MCCB A/V scores** are associated with APS MEM sensitivity⁷³, and thus may predict clinical outcome (Aim 2); 3. **EEG** measures of early auditory information processing variably predict response to early APS learning⁸⁷, MEM-enhanced APS learning⁷⁴, and TCT outcomes³¹. EEG/ERPs are acquired via 64-channel recording systems and assessed in the same order, as per^{49,107}: MMN/P3a/Theta power/Phase locking (25 min; Oddball Paradigm), ASSR (6 min). 4. **Auditory discrimination**: Words-In-Noise (WIN; NIH Toolbox) and Speech-In-Noise (Quick-SIN; Etymotic Research) are acquired at Tests 1-2, TCT hour 30 and week 22. Both measures assess the ability to recognize speech over background noise, mimicking a conversation in a noisy environment, and are thought to index peripheral (WIN) vs. more central (QuickSIN) auditory processing. MEM-enhanced APS learning may predict PACT outcome (Aim 2); gains in auditory discrimination over 30 hours of TCT, and their augmentation by MEM, will be tracked to inform evolving models of PACT mechanisms. **Predictions:** First and foremost, **target engagement (MEM-enhanced APS learning) will predict MEM-enhanced TCT outcomes (Aim 2) as described below**. Exploratory analyses will test **secondary** predictions: for example, high vs. low baseline P3a amplitude and faster P3a latency will predict greater target engagement (Aim 1), and greater MEM-enhanced TCT outcome (Aim 2). MEM-enhanced (Test 2 vs. 1) ERPs, auditory discrimination and neurocognitive (A/V) measures will also be explored as outcome (Aim 2) predictors; significant pre- vs. post-TCT changes in ERP source dynamics will also be examined for mechanistic characterization⁷¹. Robust biomarker predictors will be examined as moderators of both indirect and direct paths between treatment and outcome in a future Confirmatory Efficacy trial.

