Aim 1 – Confirm target engagement: The primary dependent measure of target engagement is MEM-enhanced APS learning. APS learning is defined as the reduction in Sound Sweeps APS threshold (ms) Test 1 to Test 2 assessment. Target engagement was demonstrated in Fig. 3⁷⁶, and will be confirmed if APS learning is increased by MEM (note that MEM and PBO groups are matched by Test 1 PBO performance via stratified randomized assignment). As appropriate, effect sizes and inferential statistics are based on standard regression or LME models with random intercepts. A significant interaction between contrast coded drug (PBO vs. MEM) and Test (Test 1 vs. Test 2) predictors on APS learning is a “Go” criteria and confirms target engagement.

Aim 2 – Test clinical, neurocognitive and functional impact of MEM on TCT, and its relationship to target engagement: We will determine if MEM+TCT produces greater, faster or more durable clinical, neurocognitive or functional gains from baseline, compared to PBO+TCT, over a 30-session course of TCT. A Cohen’s $d > 0.5$ for the main effect of drug (PBO vs. MEM) or drug x session (#10, 20, 30) interaction in an LME model is the primary “Go” criteria. The effect of drug assesses “greater” gains. Reverse Helmert contrasts for session assesses “faster” gains. A separate model comparing differences in outcomes at 12-weeks post-TCT assesses “more durable” gains. Secondary analyses will examine whether change in MEM-enhanced APS learning (“within-subject” target engagement; Aim 1) predicts gains in Aim 2 outcome measures.

Aim 3 – Biomarkers of MEM-induced gains: We will determine if baseline levels of specific neurocognitive or EEG-based measures, or changes in specific measures with initial MEM exposure (Test 2 vs. 1), predict greater sensitivity to MEM-enhanced neurocognitive, clinical or functional gains over 30-h of TCT. Regression analyses will assess whether specific candidate biomarkers predict MEM-enhanced gains in outcome measures.

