11. “Negative results... [will] guide further intervention development”? This R33 has clear ‘Go/No-Go’ criteria. If target engagement is not confirmed, we will conclude that this design setting is unsuitable for detecting robust MEM group effects on APS learning. Based on the data (e.g. evidence of MEM bioactivity), we will develop testable hypotheses (e.g. cohort differences) that might account for differential outcomes in the present application. Even if there are not robust MEM effects on APS learning (target engagement), it is possible that heterogeneity in MEM APS sensitivity might reflect meaningful subgroups of patients (e.g. low vs. high attention/vigilance), and that APS MEM sensitivity might still predict (correlate with) MEM enhancement of TCT therapeutic effects. In other words, a lack of a group difference (placebo vs. MEM) would not preclude the utility of MEM APS sensitivity as a predictive biomarker. Conversely, even if target engagement is confirmed, it is possible that group differences (placebo vs. MEM) in therapeutic gains might not be detected. A “valid” negative outcome (e.g. lack of positive MEM effects on outcome measures despite evidence of target engagement and adequate TCT exposure) will indicate that MEM-enhanced APS learning is not sufficient to enhance TCT effects in a clinically-defined SZ cohort. Analyses will then determine if MEM enhances TCT effects in biomarker-defined SZ subgroups. A failure to detect such subgroups would suggest a dissociation between target engagement in the first Sound Sweeps session and therapeutic benefit after 30-h of TCT.

12. This work is feasible. Our study team includes 2 Board Certified Psychiatrists (NS, YJ) with SZ clinical trial experience, a licensed Clinical Psychologist/Neurophysiologist and PI of a BBRF-funded trial of biomarker predictors of TCT in SZ patients (GL), an expert statistician with a career focus on analytic pathways from biomarkers to clinical function in SZ (MT), a UCSD SZ Research Program with a >30 y history of recruiting and testing thousands of psychosis patients in studies with ERPs and other biomarkers proposed in this R33 (published retest stability with 1-year follow-up¹⁴⁰), as well as double-blind, PBO-controlled trials of putative pro-cognitive agents (including MEM) in SZ patients and HS^{48,49,74,104}. We completed and published extensively on a 30-session clinical trial of TCT in SZ patients and with many of the same biomarkers proposed herein.

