"Go/No-Go" decisions are based on traditional statistical significance (Aim 1) and effect sizes (Aim 2). Formal statistical testing is conducted using linear mixed-effects (LME) models; hypothesis tests are 2-sided ($\alpha=0.05$). Model parameters are estimated via the R lme4 package and Cohen's d is estimated via the EMAtools package. Type I errors are minimized by constraining the number of primary analyses; secondary analyses use false discovery rate corrections.

PANSSt scores will be assessed at specific intervals. Because TCT is associated with improvements in both positive and negative symptoms, our *a priori* hypothesis is that a PACT effect will be evident in both positive and negative symptoms. Hence, PANSSt is used as the primary metric of symptomatic gains. A greater reduction in PANSSt score will be detected using data from baseline through TCT 30h, by a significant main effect of group (arm) or a significant interaction of group x session, with post-hoc contrasts revealing significant group differences at TCT 30h. A faster reduction in PANSSt scores will be detected using these same data by a significant interaction of group x session and a significant group difference at a point prior to TCT 30h. A more durable reduction in PANSSt scores will be detected using data from TCT 30h through 12 weeks post-TCT, by a significant main effect of arm or a significant interaction of group x post-TCT day, with post-hoc contrasts revealing significant group differences 12 weeks post-TCT.

Comparable analytic approaches will be used for neurocognition (MCCBc) and function (WHODAS) as described in "Research Strategy". Data will be described as means with SEM. Tests for normalcy will be applied to all data and non-parametric comparisons will be used if normalcy is not demonstrated. The Analysis Set for these data will be all subjects who have completed 30h of TCT and post-TCT clinical, neurocognitive and function assessments. When appropriate, missing data are handled via multiple imputation or full information maximum likelihood estimation.

Secondary regression analyses assess the predictive value of putative biomarkers on clinical, neurocognitive or functional gains from the addition of MEM to TCT. Future studies with larger samples will assess potentially more informative models, e.g. Path Analysis to study moderating effects of APS MEM sensitivity and biomarkers on both indirect (moderated-mediation) and direct paths between treatment and outcome.

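### Failing to find biomarker-defined subgroups with 36 to 54 patients cannot support the conclusion that target engagement and benefit are dissociated

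*Combined protocol and SAP*

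**What the plan says.** The inference is in item 11 of the Research Strategy, on what negative results would teach. The second half of that item takes the case where target engagement is confirmed, training exposure is adequate and memantine still shows no benefit on the outcomes. The next step is: "Analyses will then determine if MEM enhances TCT effects in biomarker-defined SZ subgroups". The item ends: "A failure to detect such subgroups would suggest a dissociation between target engagement in the first Sound Sweeps session and therapeutic benefit" after the full course of training.

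The analysis method is given in two other places. Data Analysis, Aim 3: "Regression analyses will assess whether specific candidate biomarkers predict MEM-enhanced gains in outcome measures". Section 4.4: "Secondary regression analyses assess the predictive value of putative biomarkers on clinical, neurocognitive or functional gains from the addition of MEM to TCT". Neither names a marker-by-arm term, a cutpoint or a precision target. The Specific Aims label Aim 3 as exploratory ("Explore biomarkers of memantine-induced gains"), and secondary analyses carry a false discovery rate correction. Both Power analyses paragraphs size Aim 1 only.

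**The concern.** A non-significant search tells the reader something only if the search could have found what it was looking for. Item 11 gives a failed search a mechanistic meaning: learning gains in the first session do not carry through to benefit, even in selected patients. It does not ask whether the data could have shown otherwise. Item 10 concedes that the sample will not easily give significant group differences. An interaction is generally harder to detect than a group difference of the same size, yet item 11 does not repeat the caution.

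Aim 3 is meant to choose markers for the confirmatory trial. A null result read as a dissociation could retire a useful marker, or the target itself, on data compatible with a moderate moderator.

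**Working it through.** **The plan's own figure.** The stated sample size is 27 per arm for Aim 1 (d=0.5, 80% power, two-sided 5%, test-retest correlation 0.8). Taking a change score over two tests, the variance is 2(1−0.8)=0.4, and n = 2×0.4×(1.960+0.842)²/0.5² = 25.1, or 26 per arm. With the t distribution, power is 79.8% at 26 and 81.3% at 27, so 27 is reproduced. It covers the Aim 1 drug effect and says nothing about Aim 3.

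**Inputs.** N=54 is the randomised number. N=36 is the expected number of completers (18 per arm, Subject throughput); it matters because section 4.4 defines the analysis set as those who finish 30 hours and the post-training assessments. The moderator size b is the change in the arm effect, in residual SDs, per SD of marker. The documents give none, so b = 0.4, 0.5 and 0.6 are assumptions.

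**Standard error and interval.** Let y = β₀ + β₁t + β₂x + b·t·x + e, with t = ±½, x standardised and residual SD 1. Then SE(b) ≈ 2/√N.

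- N=54: SE = 0.272; half-width = 2.009×0.272 = 0.55.
- N=36: SE = 0.333; half-width = 2.037×0.333 = 0.68.

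Simulated averages are slightly wider, about 0.57 and 0.73.

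**Power, marker kept continuous.** Noncentral t with N−4 degrees of freedom and noncentrality b√N/2; simulated values (6,000 trials per setting) in brackets.

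| b | N=54 | N=36 |
|---|---|---|
| 0.4 | 30.2% (28%) | 21.4% (20%) |
| 0.5 | 43.7% (40%) | 30.7% (29%) |
| 0.6 | 58.0% (55%) | 41.5% (38%) |

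Non-detection is the likelier result in five of the six cells. By the formula, 80% power needs b of about 0.78 (N=54) or 0.96 (N=36). For b=0.5 it needs N = 4×(1.960+0.842)²/0.5² ≈ 126.

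**Scale.** If the average drug effect is zero, b=0.5 puts patients one SD above the marker mean at an arm effect of d=0.5, the plan's own Go threshold. With a half-width of 0.55, even an estimate of exactly zero at N=54 would not exclude it.

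**What a split would add.** Cutting a normal marker at its median keeps 2/π = 63.7% of the information and loses 36.3%. Simulated power at b = 0.4, 0.5 and 0.6 would then be 20, 28 and 37% (N=54), or 15, 20 and 26% (N=36).

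**The case against.** A reader might infer that the plan cuts its markers into high and low groups and that this is why a real moderator would be missed. The documents do not support that.

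- The named method is regression, in both places that state one, and no cutpoint appears anywhere.
- The P3a wording ("high vs. low baseline P3a amplitude and faster P3a latency will predict greater target engagement") is one exploratory example and reads naturally as a direction.
- The attention/vigilance wording ("e.g. low vs. high attention/vigilance") belongs to the other branch of item 11, where target engagement is not confirmed, and that sentence goes on in terms of correlation.
- The cut on "high/low Test 1 (baseline) APS learning" is a randomisation stratum, not an Aim 3 analysis.

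Nor would a split be the main cause: power is already about 20 to 55% without one. What remains is that the subgroup wording is not tied to the regressions, so a split is neither planned nor ruled out.

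Three further points favour the plan. First, the inference is hedged (it would only suggest), Aim 3 is exploratory, and a Go decision does not require a biomarker. That limits the harm, but the sentence still gives a null result a meaning it cannot carry. Second, the percentages assume one outcome value per patient, whereas the trial measures at baseline and at sessions 10, 20 and 30 and uses mixed models. That is fair: they are not this trial's exact power. But for a slope of 0.5 raw SD to reach 80% power, the residual SD would have to fall to about 0.5/0.78 = 0.64 of the raw SD at N=54, or 0.5/0.96 = 0.52 at N=36. False discovery rate correction works the other way. Third, a large moderator could be found: at b=0.8 and N=54 the formula gives about 82% with a continuous marker and 63% with a median split. Non-detection is therefore not the likely result for every moderator.

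**Conclusion.** The concern holds for the inference at the end of item 11. For an assumed slope difference of 0.4 to 0.6 SD per SD, detection is about 28 to 55% likely with 54 patients and 20 to 38% with 36, with the marker continuous and before correction for multiple testing. With intervals reaching about 0.55 and 0.7 SD either side of the estimate, a null search is inconclusive about moderate moderators and is not evidence of a dissociation. These figures assume a normal marker, a linear relation, equal arms and one outcome value per patient.

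The stronger claim, that planned dichotomisation makes the search fail, does not hold. No split is planned; a median split would make detection worse, but sample size is the main cause. The point is minor in cost and does not touch the Go rule. It changes what the trial may conclude from a negative Aim 3.

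**What to change.** Replace the last sentence of item 11 with a statement to this effect: failure to find a moderator will be treated as inconclusive unless the 95% confidence interval for the marker-by-arm interaction excludes differences large enough to matter, with that size set by the sponsor before unblinding.

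In Data Analysis (Aim 3) and section 4.4, state that the item 11 subgroup search is carried out through the regressions already planned. Each candidate marker enters as a continuous value with a marker-by-arm term, reported as an estimate with its 95% interval. High and low groups are for display only.

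The cost is a few sentences, with no extra patients or assessments. There are two small downsides. A continuous term assumes a roughly linear relation, which a plot can check. And a negative result will support a less definite conclusion: with 36 to 54 patients the interval will seldom exclude moderate moderators.

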4.1. Brief Summary

Current therapies for chronic psychotic disorders such as schizophrenia include antipsychotic medications, which do not significantly improve function or correct cognitive deficits in this disorder, and cognitive therapies, which produce only modest benefits to most patients. We hypothesize that medications that specifically target neurocognitive processes like attention and vigilance will significantly augment the clinical benefits of cognitive therapies in schizophrenia. Here, we will confirm that the pro-cognitive medication, memantine, enhances learning of an auditory processing task in a computerized targeted cognitive training (TCT) program in antipsychotic-medicated schizophrenia patients, and complete a randomized, double-blind clinical trial in antipsychotic-medicated schizophrenia patients, comparing TCT (30 sessions) plus memantine (MEM) vs. TCT (30 sessions) plus placebo (PBO).

4.2. Study Design

4.2.a. Narrative Study Description

Screened, eligible patients complete clinical, neurocognitive and functional measures and candidate biomarkers (EEG, QuickSIN, WIN). Aim 1 is completed in 2 tests, approximately 1 week apart. In Test 1, Sound Sweeps are tested after PBO for all subjects, who are then randomized to TCT+PBO vs. TCT+MEM arms (n=27/arm) using stratified random sampling (over sex, age and high/low Test 1 APS learning) blind to arm identity, similar to our previous studies. Test 2 follows approximately 5-7 d later; this test is identical to Test 1, except that subjects receive their assigned study drug (PBO vs. MEM (20 mg po) 1 hour prior to Sound Sweeps. Tests 1 and 2 are used to assess target engagement (Aim 1: MEM-enhanced APS learning) and MEM effects on auditory discrimination (QuickSIN, WIN). Our design allows for 20% attrition from enrollment (n=69) to completion of target engagement testing (n=54). For Aim 2, TCT in these same subjects is scheduled 3 d/week (M-W-F) for 1-h/d, recognizing the need for flexibility (T-Th are "make-up days"), and continues until a subject completes 30-h (approximately 10-12 weeks). TCT is delivered by trained staff. 60 min prior to each TCT session, patients take either PBO or 20 mg MEM, as per arm assignment. Patients and staff are blind to study arm; staff are blind to patients' baseline or post-intervention assessments. Outcome metrics assess symptom, neurocognitive and functional changes after 10, 20 and 30 TCT sessions, and 12 weeks post-TCT. Candidate biomarkers are re-tested after completion of 30 sessions of TCT.

4.2.b. Primary Purpose

Treatment

4.2.c. Interventions

Type	Name	Description
Behavioral (e.g., Psychotherapy, Lifestyle Counseling)	Targeted Cognitive Training (TCT)	Thirty, one-hour sessions over approximately 10 weeks, of computerized cognitive training modules.
Drug (including placebo)	memantine	The pro-cognitive medication, memantine (placebo vs. 20 mg) will be administered orally, 1 hour prior to targeted cognitive training, in a double-blind, randomized design.

4.2.d. Study Phase

Phase 2/3

Is this an NIH-defined Phase III Clinical Trial?

Yes No

4.2.e. Intervention Model

Parallel

4.2.f. Masking

Yes No

Participant Care Provider Investigator Outcomes Assessor

4.2.g. Allocation

Randomized

